## 5 Selection of participants

Adult asthenozoospermic, oligozoospermic or oligoasthenozoospermic males who come to the Uroandrology unit of “Hospital Clínic de Barcelona” of Barcelona.

### 5.1 Inclusion criteria

- Age: 18 to 45
- Male patients with idiopathic infertility classified with asthenozoospermia, oligozoospermia or oligoasthenozoospermia after seminal assessment.
- Not achieving pregnancy after at least one year of intercourse with the same partner without protective measures

### 5.2 Exclusion criteria

- Azoospermia (absence of spermatozoa) or severe oligozoospermia ( $< 5 \times 10^6$  spermatozoa/ml of ejaculate)
- Testicular torsion or prostatitis
- Urinary retention and infections
- Drug consumption
- Hormone treatments
- Recent surgical interventions
- Diabetes
- Kidney or liver disease
- Leukocytosis
- Antioxidant supplement consumption in the last 3 months
- $BMI > 30 \text{ Kg/m}^2$
- Endocrinopathies, hypo and hyperthyroidism
- Chromosomal anomalies (XX, XYY, XXY)
- Treatments with anticoagulants
- Radiotherapy/Chemotherapy
- Participation in another clinical study prior to inclusion in this study that could affect the objectives of the current study

## 6 Treatment and study calendar

The investigator will recruit the patients as they come to consultation and meet the inclusion and exclusion criteria. The assignment of the study treatment will be carried out randomly.

The expected duration for the recruitment of patients will be 1 year. After the patient recruitment, they will attend to 3 visits (initial visit, 3 months and 6 months visits).

### 6.1 Baseline Visit (V0)

In this visit the patients will sign the informed consent form (if they agree to participate in the study) after reading the patients information sheet and receiving all the information about the study by investigators. The investigator will ensure that patients meet all the inclusion/exclusion criteria in order to be finally included in the study. The investigator will give to the patients the product needed until the next visit.

In order to characterize the population of patients, the following demographic parameters will be collected in this visit:

- Age
- Studies and degrees
- Weight, height and BMI
- Professions
- Infertility period
- Years of marriage
- Physical activity
- Smoking history
- Blood analytics, to determine hormones (testosterone, Prolactin, FSH, LH, inhibin)

Semen samples will be collected in order to do the following analysis:

- Seminal analysis as described in the manual of the WHO 2010 (15)
- Sperm DNA fragmentation
- SORP
- Sperm ROS intracellular and sperm DNA oxidation

Semen samples will be obtained as described in the manual of the WHO 2010 section 2.2 (15) but after a minimum of 3 days and a maximum of 5 days of sexual abstinence. The sample will be taken by masturbation and ejaculated into a clean, wide-mouthed container that has been confirmed to be non-toxic for spermatozoa, administered by the hospital. The total ejaculated sample will be delivered between 30-45 minutes maximum after the collection. Prior to collection, a thorough hand wash will be required. The investigator will be responsible for the samples, both in the custody and conservation. After the sample extraction a code will be assigned which will be the only identification of the sample, thus ensuring confidentiality of the data in accordance with the provisions of the LOPD. Once the sample has been used for research purposes, it will be destroyed; so, it won't be preserved.

The results of the hormones will be taken from the habitual blood analysis that take place in routine clinical practice.

A double-blind randomized placebo-controlled clinical study to verify the efficacy of TetraSOD® in the improvement of semen quality in patients with idiopathic infertility.

- Seminal analysis will be performed as described in the manual of the WHO 2010[16].
- Sperm DNA fragmentation will be performed using COMET assay.
- SOPR will be measured by the Mioxsys technique.
- Sperm ROS intracellular and sperm DNA oxidation will be measured by flow cytometry evaluating the sperm intracellular ROS (superoxide anion, hydroxyl radical, hydrogen peroxide) and 8-hydroxydeoxyguanosine (8OHdG) concentrations, respectively.

## 6.2 3 months Visit (V3months)

During this visit semen samples will be collected as was done at V0. The following analyses will be performed:

- Semen analysis as described in the manual of the WHO 2010 (15)
- Sperm DNA fragmentation
- SORP
- Sperm ROS intracellular and sperm DNA oxidation
- Blood analytics, to determine hormones (testosterone, Prolactin, FSH, LH, inhibin)

The analyses will be performed as described in V0.

Adverse events attributable to the treatment will be recorded.

Patients will be asked to stop the treatment.

## 6.3 6 months Visit (V6months)

During this visit semen samples will be collected as was done at V0. The following analysis will be performed:

- Semen analysis as described in the manual of the WHO 2010 (15)
- Sperm DNA fragmentation: if an improvement of this parameter is not detected in V3, it will not be evaluated at this visit.
- SORP
- Sperm ROS intracellular and sperm DNA oxidation: if an improvement of this parameter is not detected in V3, it will not be evaluated at this visit.
- Blood analytics, to determine hormones (testosterone, Prolactin, FSH, LH, inhibin)

The analyses will be performed as described in V0.

Adverse events attributable to the treatment will be recorded.

A double-blind randomized placebo-controlled clinical study to verify the efficacy of TetraSOD® in the improvement of semen quality in patients with idiopathic infertility.

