**Table 1: study schedule**

	V0	V3 months	V6 months
Inclusion/exclusion criteria	x		
Sign Informed consent	x		
Delivery of product	x		
Sociodemographic data	x		
Semen samples collection	x	x	x
Seminal analysis	x	x	x
Sperm DNA fragmentation	x	x	x*
Static Oxidation Reduction Potential	x	x	x
Sperm ROS intracellular and sperm DNA oxidation	x	x	x*
Hormones	x	x	x
Collection of excess product and empty blisters		x	
Adverse events**		x	x

\* If an improvement of this parameter is not obtained in V3, it will not be evaluated at this visit.

\*\* Adverse events will be collected from the first intake of the product and during the 6 months of the study.

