### 7.2 Statistical analysis

A descriptive statistic of all the variables collected will be made.

The categorical variables will be presented in the form of lists of frequencies and proportions. For the quantitative variables, central tendency (mean and median) and dispersion (standard deviation, maximum and minimum values) will also be presented.

A double-blind randomized placebo-controlled clinical study to verify the efficacy of TetraSOD® in the improvement of semen quality in patients with idiopathic infertility.

Initial demographic and anthropometric characteristics of patients in TetraSOD® and placebo groups will be compared with independent t-test for continuous variables and chi square test for categorical ones. The non-parametric Mann-Whitney test will be applied to evaluate the effects of the dietary supplementation with TetraSOD® group vs. placebo group at the same time of study (time 0, 90 d or 180 d). Within each experimental group (TetraSOD® and placebo), the non-parametric Friedman test for matched-pairs will be applied in order to determine statistically significant differences of data recorded at the three sampling times (0, 90 d and 180 d). Significance will be accepted for  $p < 0.05$ . All analyses will be conducted with Prism 6 software.

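### The 6-month DNA fragmentation and ROS/DNA oxidation assays depend on an undefined 3-month improvement; read per patient, this invalidates the planned three-time Friedman tests on these secondary outcomes

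*Combined protocol and SAP*

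**What the plan says.** Section 6.3 lists the 6-month assays. WHO semen analysis and sORP are unconditional. DNA fragmentation and intracellular ROS/DNA oxidation each carry the condition "if an improvement of this parameter is not detected in V3, it will not be evaluated at this visit". The Table 1 footnote repeats it: "If an improvement of this parameter is not obtained in V3, it will not be evaluated at this visit". Neither place gives a threshold, and neither says whether the decision is taken for a patient, an arm or the trial. Table 1 has semen collected from every man at V6 regardless.

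Section 7.2 makes no allowance for the condition. "Within each experimental group (TetraSOD® and placebo), the non-parametric Friedman test for matched-pairs will be applied", to test "differences of data recorded at the three sampling times (0, 90 d and 180 d"). Between arms, "The non-parametric Mann-Whitney test will be applied to evaluate the effects of the dietary supplementation" at each of the same three times. The significance level is 0.05. No missing-data rule is given.

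On timing, section 6 states: "The expected duration for the recruitment of patients will be 1 year".

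**The concern.** Whether the third value exists depends on how the second compares with the first. A test that needs all three values then runs on a sample chosen for showing a fall from V0 to V3, and that fall is part of what the test is meant to detect. The 180-day between-arm test would compare the men who improved in one arm with the men who improved in the other, which is no longer the randomised comparison.

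Sperm DNA integrity and oxidative stress are named secondary objectives (section 3.2). If the rule works per patient, the within-arm results for these assays could be reported as a treatment response when they would arise with an inert product.

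**Working it through.** **Inputs.** From the documents: three times, a within-arm Friedman test at 0.05 (section 7.2), 50 men per arm and 20% drop-out (section 7.1), and 1 year of recruitment (section 6). That leaves 50 × 0.8 = 40 evaluable men per arm. The documents give no between-visit correlation, effect size or improvement threshold for these assays, so those below are assumptions. Lower values count as better.

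**The plan's own figure.** The plan states no error rate for the Friedman test. Its sample size reproduces: 2 × [25 × (2.576 + 0.842)/20]² = 36.5, and 36.5/0.8 = 45.6, rounded up to 46. It concerns sperm count and does not bear on this point.

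**Per-patient rule, Friedman test.** With three times, Q = n × Σ(mean rank − 2)², compared with 5.991 (chi-square, 2 df).
- Every man with complete data has V3 < V0, so his V0 rank is at least 1 above his V3 rank. The mean ranks therefore differ by at least 1.
- The smallest possible sum of squares is 0.5² + 0.5² + 0² = 0.5, so Q ≥ n/2.
- At n = 12, Q ≥ 6 > 5.991. Rejection is certain whatever the V6 values are.
- With no effect and exchangeable visits, half the men qualify: about 20 of 40. The three possible rank orders (V0, V3, V6) are (2,1,3), (3,1,2) and (3,2,1), equally likely. The expected mean ranks are 8/3, 4/3 and 2, so Q is about n × 8/9 = 17.8 at n = 20.
- Exact enumeration with 40 men per arm gives a false-positive rate above 99.99%. Simulation (5,000 trials per setting; 37, 40 or 50 men; equal correlation 0, 0.5 and 0.8, serial correlation 0.5 and 0.8) gives at least 99.9%, and both arms reject together.
- A stricter threshold (a fall of more than 0.5 SD) still gives 90% to 100%.
- If every man is measured, the rate is 4.2% to 5.5%.
- At correlation 0.5 the change V3 − V0 has SD √[2(1 − 0.5)] = 1. Selected placebo men then show a mean spurious fall of √(2/π) = 0.80 SD.

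**Per-patient rule, 180-day Mann-Whitney test.**
- With no effect, the error rate is 4.4% to 5.2%.
- With an assumed uniform, persistent 0.8 SD effect, 40 men per arm and equal correlation 0.3 to 0.7, power falls from 93% to about 75%.
- The estimated 0.8 SD difference is unbiased under equal correlation (0.80) and attenuated under serially decaying correlation (0.66 to 0.73).
- If instead half the treated men respond by 1.6 SD (mean 0.8), it is estimated as about 0.92 to 1.05 SD. The direction of bias is not fixed.

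**Trial-level rule (everyone or no one re-measured).**
- If the criterion is a lower mean at V3, the Friedman test rejects in 2.1% to 2.9% of null trials overall, and in 4.1% to 5.9% of those that meet the criterion.
- If the criterion is a roughly significant fall, it rejects in 0.6% to 1.1% overall, but in about 26% to 38% of those that meet it.

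**Timing.** The last V3 visit falls at about month 12 + 3 = 15. A man entering at month t has V6 at t + 6, which is before month 15 when t < 9. With even recruitment, 9/12 = 75% of V6 visits precede the last V3 result.

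**The case against.** A reader might infer that the plan as written must produce false significance. The documents do not support that. Both statements of the rule refer to improvement of the parameter and never say in which patient. An all-or-none rule for the assay is a possible reading, and under it the overall Friedman error stays below 5%. This stands, and the finding of certain rejection is therefore tied to the per-patient reading. That reading is still the better fit: the rule sits in the description of one man's visit, and most V6 visits would come before a trial-level decision could be made.

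A reader might also infer that a trial-level decision would have to use partial or unblinded data. That does not follow. Section 10 says samples will be stored for possible later analysis, so V6 samples could be held until the last V3 result. Section 6.1, however, says samples are destroyed after use. The two sections conflict, so storage can be neither relied on nor ruled out. Nothing in the documents suggests unblinding; section 4 keeps the sequence visible only to the study monitor.

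Nor does the selection manufacture a between-arm effect. The spurious Friedman signal appears in placebo as well, and the 180-day Mann-Whitney test holds its level when nothing works.

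Finally, these are secondary outcomes. The main objective is at 3 months, all the assays are done in everyone at V0 and V3, and V6 follows a wash-out. This is correct and limits the importance of the point, but it does not make the affected analyses valid.

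**Conclusion.** The point holds as an undefined measurement rule that conflicts with the analysis applied to it. Under the per-patient reading, the within-arm three-time Friedman tests on DNA fragmentation and ROS/DNA oxidation carry no information about treatment: rejection is certain from 12 complete men per arm, and about 20 are expected with no effect. That bound needs no assumption about correlation or V6 values, only that improvement means V3 better than V0. The 180-day Mann-Whitney test keeps its null error rate but loses power and can be biased in either direction. The sizes given for it depend on assumed effects and correlations.

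Under a trial-level rule the overall error is not inflated. Results that pass a significance-type criterion would still be selectively favourable (about 26% to 38% significant under the null), and the rule could be applied only with an unplanned interim look or stored V6 samples.

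The 90-day comparisons, the WHO semen parameters and sORP are unaffected. This should be fixed, but it does not threaten the main objective.

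**What to change.** Preferred: delete the condition in section 6.3 and the asterisk and footnote in Table 1, and run these assays on every V6 semen sample in both arms. The samples are collected anyway. The cost is at most one extra run per assay per man; the documents do not give the price. This restores the Friedman error rate to its nominal level.

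Otherwise: drop these V6 assays for everyone, remove these outcomes from the three-time Friedman and 180-day Mann-Whitney analyses in section 7.2, and base conclusions on the 90-day between-arm comparison in all randomised men. This has no assay cost, but gives up information on these outcomes after wash-out.

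If a trial-level rule is what was intended, wording alone could state it: name the decision unit, define the criterion, and exclude these outcomes from the three-time Friedman test. That works only if V6 samples are kept, or an interim look is planned.

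In any case, reconcile sections 6.1 and 10 on whether samples are destroyed or stored. Settle the change before the first V6 visit, because assays skipped by then may not be recoverable.

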**Table 1: study schedule**

	V0	V3 months	V6 months
Inclusion/exclusion criteria	x		
Sign Informed consent	x		
Delivery of product	x		
Sociodemographic data	x		
Semen samples collection	x	x	x
Seminal analysis	x	x	x
Sperm DNA fragmentation	x	x	x*
Static Oxidation Reduction Potential	x	x	x
Sperm ROS intracellular and sperm DNA oxidation	x	x	x*
Hormones	x	x	x
Collection of excess product and empty blisters		x	
Adverse events**		x	x

\* If an improvement of this parameter is not obtained in V3, it will not be evaluated at this visit.

\*\* Adverse events will be collected from the first intake of the product and during the 6 months of the study.

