## 7 Statistical analysis

### 7.1 Sample size

The sample size has been calculated using the on-line tool GRANMO v7.12 (<https://www.imim.es/ofertadeserveis/software-public/granmo>). Data obtained in the previous pilot trial regarding total sperm count per ejaculate were used as a reference. With the aim to determine differences between the mean of the two experimental groups, and accepting an alpha risk of 0.01 and a beta risk of 0.2 in a two sided test, a total of 46 individuals per group are necessary to recognize as statistically significant a difference greater than or equal to  $20 \times 10^6$  spermatozoa/ml of ejaculate. The common standard deviation is assumed to be 25 (the maximum value in the previous pilot trial), with an anticipated drop-out rate of 20%. In that way, a total of 100 subjects, 50 per experimental group, will be recruited for the present clinical trial.

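### Adverse events are promised from first intake, but no contact is described for men who leave before the 3-month visit, so up to 20 of 100 may leave no safety record

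*Combined protocol and SAP*

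**What the plan says.** Safety is a secondary objective in section 3.2, and section 2.2 also names it alongside efficacy in describing the study's main aim.

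The collection period is set in the footnote to Table 1: "Adverse events will be collected from the first intake of the product and during the 6 months of the study". In the table itself, the row "Adverse events" is marked at the 3-month visit (V3) and the 6-month visit (V6) and nowhere else. Sections 6.2 and 6.3 each carry the sentence "Adverse events attributable to the treatment will be recorded".

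On contacts, section 6 says of recruited patients that "they will attend to 3 visits (initial visit, 3 months and 6 months visits". Section 6.1 has the investigator hand over at baseline enough product to last to the next visit. Table 1 shows no other delivery and puts the return of leftover product and blisters at V3 only.

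On drop-out, section 7.1 plans "with an anticipated drop-out rate of 20"%, with no timing and no cause, and states that "a total of 100 subjects, 50 per experimental group, will be recruited".

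On men who leave, the only text is in section 9, and it concerns keeping their data. Section 7.2 promises descriptive statistics for all variables but does not say which men form the denominator for adverse events.

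**The concern.** The footnote sets a period; the schedule supplies two occasions for asking. The first contact described after baseline is V3, when treatment ends. No diary, telephone call, early-termination visit or note of why a man stopped is described. A man who stops in the second week and does not come back falls inside the promised period, yet no step in the plan would reach him.

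This loss may be selective. A man who stops because the product disagreed with him has an event that matters for safety, and he is also among those least likely to be asked. Once he has gone, analysis may not be able to restore the information. With no reasons for stopping on file, the sponsor could neither show nor rule out that intolerance played a part.

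The point is separate from the limitation of recording to attributable events. Removing that limitation would still not reach these men.

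**Working it through.** **1. The plan's own figure.** Inputs from section 7.1: difference 20, SD 25, and "accepting an alpha risk of 0.01 and a beta risk of 0.2 in a two sided test". By the normal approximation:

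n = 2 × [25 × (2.576 + 0.842) / 20]² = 36.5 evaluable men per group.

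Allowing for 20% drop-out: 36.5 / 0.8 = 45.6, so 46. This matches "a total of 46 individuals per group are necessary". (Rounding to 37 before inflating gives 37 / 0.8 = 46.25, so 47.) The 46 therefore already contains the drop-out. The number who will take product is the 50 per group to be recruited, and that is the base used below.

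**2. How many men could go unasked.** Expected drop-out is 20% × 100 = 20 men, or 10 per arm if equal. A man who leaves after V3 has already been asked at V3 about his whole treatment period. Only those who leave before V3 miss both occasions. The share leaving before V3 is not stated, so it is varied:

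| Share of drop-outs leaving before V3 (assumed) | Men with no enquiry, of 100 |
|---|---|
| 0% | 0 |
| 25% | 5 |
| 50% | 10 |
| 75% | 15 |
| 100% | 20 |

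**3. Effect on the recorded rate in one arm.** Assumptions: 50 men take the product in the active arm and 4 men have a recorded event. Let m be the number leaving before V3 and p the share of them who had an event.

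True rate = (4 + p × m) / 50. Share of affected men missed = p × m / (4 + p × m).

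| m | p | Affected men | True rate | Missed |
|---|---|---|---|---|
| 5 | 0% | 4 | 8% | 0% |
| 5 | 25% | 5.25 | 10.5% | 24% |
| 5 | 50% | 6.5 | 13% | 38% |
| 10 | 0% | 4 | 8% | 0% |
| 10 | 25% | 6.5 | 13% | 38% |
| 10 | 50% | 9 | 18% | 56% |

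The recorded figure depends on the denominator. Over all 50 it is 4/50 = 8%. Over men actually asked it is 4/45 = 8.9% for m = 5 and 4/40 = 10% for m = 10. On the second basis the rate is too low only when p exceeds the rate among men asked, as it does in the 25% and 50% rows.

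**4. Effect on the comparison between arms.** If both arms lose the same number of affected men, the difference in counts is unchanged. Suppose instead that 10 men leave each arm before V3, and 25% of them in one arm and none in the other had an event. Then 2.5 affected men are missing from one side only, and the difference in rates over 50 per arm is off by 2.5/50 = 5 percentage points.

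**5. Precision.** If no events are seen, the one-sided 95% upper bound is 1 − 0.05^(1/n): 5.8% for n = 50 and 7.2% for n = 40. The 7.2% also assumes that the men who left resemble those who stayed, which fails if intolerance made them leave.

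**The case against.** Four objections have weight.

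- **The footnote covers the whole period.** A reader might infer that the plan limits collection to two dates. It does not. For men who attend, the V3 enquiry can reach back to first intake and the V6 enquiry covers the rest, although it relies on recall over about three months. This stands. The gap concerns men who do not attend.
- **The 20% is an upper bound.** A reader might infer that a fifth of the men will have no safety record. Section 7.1 gives neither timing nor cause, so that follows only if every drop-out precedes V3. This stands, and the range must begin at zero.
- **Bias between arms is not established.** A reader might infer that the comparison is pulled towards no difference. That requires intolerance to cause drop-out, and to do so more in one arm. The documents give no reasons for drop-out, and section 7.2 sets out no test specific to adverse events. This stands; the distortion is conditional.
- **Silence is not proof.** Patients receive an information sheet, and the consent and contact pages were not available for this review. A route for reporting problems between visits may be described there. This stands in part: the claim is that the protocol's visit sections and schedule describe no such procedure, not that nobody would ever ask. A number to ring would also not amount to a planned enquiry at withdrawal with a recorded reason.

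None of these supplies a step that reaches a man who leaves before V3.

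**Conclusion.** The gap is real and worth correcting. The plan promises collection from first intake and describes no means of obtaining it from men who leave before V3. Between 0 and 20 of 100 men could be affected at the assumed 20% drop-out; the documents do not allow a narrower figure.

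If some of these men stopped because of an event, the count of affected men is too low. In the illustration the true rate is 8% to 18%, against 4 recorded in 50 (8%). That range rests on an assumed 4 recorded events, 5 or 10 men leaving before V3, and 0% to 50% of them affected; none of these inputs is in the documents. Distortion of the comparison between arms is possible but needs such stopping to differ by arm. The sample size is not affected.

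**What to change.** **Section 6 and Table 1.** Add one end-of-participation contact, for which a phone call is enough, for any man who stops the product early or misses V3. Record events since first intake, date of last capsule and reason for stopping.

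**Section 7.2.** Report adverse events by arm in all randomised men who took at least one capsule, state how many in each arm were never reached, and list reasons for stopping by arm.

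**Cost.** Protocol wording and, at the assumed drop-out, at most about 20 calls by existing staff. Some men will remain unreachable, which is why their number should be reported. Recorded event rates may be slightly higher. A dated event card given out with the capsules could improve recall in men who return, but it is optional and does not address this gap.
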